3.4.3 Secondary Endpoints

Immunogenicity

The immunogenicity parameters will be calculated with their 95% CIs using the exact binomial distribution (Clopper-Pearson method) for proportions and using normal approximation of log-transformed for GMTs and GMTs ratio. The 95% CI of proportions difference (ie, difference between vaccine groups in SC) will be calculated using Wilson Score method without continuity correction. All analyses will be conducted by study group.

In particular, the following descriptive statistics will be displayed:

- GMTs of individual HAI titer on D01 and 28 days after the last vaccination (D29 or D57)
- Percentage of participants with detectable HAI titer, ie, with a titer ≥ 10 (1/dil) at D01 and 28 days after the last vaccination (D29 or D57)
- GMs of Individual HAI titer ratio: 28 days after the last vaccination (D29 or D57) / D01
- SC rates (titer < 10 [1/dil] at D01 and post-injection titer ≥ 40 [1/dil] at D29 or D57, or titer ≥ 10 [1/dil] at D01 and a ≥ 4-fold-rise in titer [1/dil] at D29 or D57)
- Percentage of participants with titers ≥ 40 (1/dil) on D01 and 28 days after the last vaccination (D29 or D57)

• The RCDCs of pre-vaccination titer prior to the first vaccination (D01), and post-vaccination titer at D29 after last vaccination will be generated for each study group. The RCDCs will include the plots of the 2 study groups the same figure.

The analysis will be conducted for each immunogenicity variable on the PPAS, and on FAS if the attrition rate from FAS to PPAS is greater than 10%.

In addition, subgroup analysis will be performed; in particular, immunogenicity will be described according to season, sex, race, previous influenza vaccination status (received a seasonal influenza vaccine in the last past influenza season or not), baseline seropositivity status (seropositive and seronegative are defined as baseline antibody titer $\geq 1:10$ or < 1:10), and age subgroups (3 to 5 and 6 to 8 years) as appropriate according to number of participants in the respective subgroups. Subgroup analyses will be performed on PPAS.

Safety

For the main safety parameters, 95% CIs of point estimates will be calculated using exact binomial method (Clopper-Pearson method) for single proportions and using the normal approximation for quantitative data.

All analyses will be descriptive; no hypotheses will be tested.

The number of participants with documented safety will be used as denominator of the frequencies.

For solicited reactions, the denominator will be the total number of participants who have nonmissing data for the endpoint considered.

For unsolicited AEs, the denominator will be the total number of participants who were vaccinated.

In terms of contents, solicited reactions will be presented by time to onset, maximum severity, number of days of occurrence and action taken; unsolicited AEs will be presented by causal relationship, time of onset, maximum severity and duration; SAEs will be presented by causal relationship, seriousness and outcome.

Subgroup analyses will also be performed; in particular, the main safety endpoints will be described according to age subgroups (3 to 5 and 6 to 8 years), previous vaccination status, sex and race, as appropriate according to number of participants in the respective subgroups.

3.4.4 Exploratory Endpoint

The immunogenicity parameters will be calculated with their 95% CIs using the exact binomial distribution (Clopper-Pearson method) for proportions and using normal approximation of log-transformed titers for GMTs. All analyses will be conducted by study group. For some parameters (eg. GMTs, 4-fold increase) difference or ratio between groups may be calculated with 95%CI. The 95% CI of ratios of GMTs or 4-fold increase rate will be calculated using the same method as for the primary objective.

Neutralizing Ab titers will be measured for each influenza strain with the SN method.

Confidential/Proprietary Information Page 21 of 40 In particular, the following endpoints will be described with 95% CIs:

- GMTs of individual SN Ab titer on D01 and 28 days after the last vaccination (D29 or D57)
- GMs of individual SN Ab titer ratio (fold increase in post-vaccination titer relative to D01) at 28 days after the last vaccination (D29 or D57)
- Percentage of participants with SN Ab titers ≥ 20 (1/dil), ≥ 40 (1/dil), ≥ 80 (1/dil) at 28 days after the last vaccination (D29 or D57)
- Percentage of participants with fold-increase in SN Ab titer (post/pre) ≥ 2 and ≥ 4 at 28 days after the last vaccination (D29 or D57)
- Percentage of participants with detectable SN Ab (SN Ab titer ≥ 10 [1/dil]) at D01 and 28 days after the last vaccination (D29 or D57)
- The RCDCs of pre-vaccination titer prior to the first vaccination (D01) and post-vaccination titer at D29, after last vaccination will be generated for each study group. The RCDCs will include the plots of the 2 groups on the same figure.

The analysis will be conducted for each immunogenicity variable on the PPAS subset (PPAS-SN) and on the FAS subset (FAS-SN) if the attrition rate from FAS-SN to PPAS-SN is greater than 10%.

In addition, as appropriate according to the number of participants in the respective subgroups, the descriptive summary of SN immunogenicity main parameters will also be produced by:

- Serological SN status at baseline (< 10 and \geq 10 1/dil)
- Previous influenza vaccination status
- Age subgroup
- Sex
- Race
- Season

3.4.5 Handling of Missing Data and Outliers

3.4.5.1 Safety

Generally, no replacement will be done for Safety Missing Data and Outliers.

3.4.5.1.1 Immediate

For unsolicited systemic AEs, a missing response to the "Immediate" field is assumed to have occurred after the 30-minute surveillance period and will not be imputed.

3.4.5.1.2 Causal Relationship

By convention, all events reported at the injection site (either solicited or unsolicited) will be considered as related to the administered product and then referred to as reactions. In the same

Confidential/Proprietary Information Page 22 of 40 way, all solicited systemic events pre-listed in the CRF are also considered as related to vaccination and will be considered as reactions.

- For unsolicited systemic AE, missing relationship will be considered as related to study vaccine(s) at the time of analysis.
- The missing relationship to study procedures for SAEs will not be imputed.

3.4.5.1.3 Intensity

For solicited reactions, missing intensities will be handled as described in Section 4.2.1.1. For unsolicited AEs, missing intensities will remain missing and will not be imputed.

3.4.5.1.4 Start Date and End Date

Missing or partially missing start dates or end dates for unsolicited AEs (including SAEs) will remain missing and not be imputed. If the start date is missing or partially missing, the time of onset will be considered missing. If either the start date or end date is missing or partially missing, the duration will be considered missing.

Missing or partially missing end dates for ongoing solicited AEs will remain missing and not be imputed.

3.4.5.1.5 Action Taken

Missing actions taken will remain missing and not be imputed.

3.4.5.2 Immunogenicity

No imputation of missing values and no search for outliers will be performed. LLOQ and ULOQ management will be performed as described in Section 4.2.3.1.

3.5 Interim Analysis

During the recruitment period of 2022-2023 season, only approximately 25% out of the 1412 targeted participants aged 3 to 8 years had been enrolled and vaccinated in the study.

Thus, it was decided to conduct an interim analysis to review safety and assess the likelihood of the study success by the end of enrollment (1412 participants) based on the immunogenicity data accumulated after randomizing and vaccinating approximatively 366 children (approximately 25% of participants).

For this interim analysis:

• A Firewall Internal Committee (FIC) including Senior members from Clinical, Safety and Biostatistics, not involved in the study conduct, will be set up to review the content of the results including the interim analysis of immunogenicity and summaries of safety and recommend if the stopping of this study is warranted

Confidential/Proprietary Information Page 23 of 40

- An unblinded statistical team will be in charge of breaking the blind of the enrolled participants after database lock, conducting the interim statistical analysis and communicating unblinded results to the FIC. Should the study continue for a second season after the results of the interim analysis, the unblinded statistical team will not be involved in the upcoming conduct of the study.
- The recommendation for stopping the study will be based on the following criteria:
 - The overall PPoS of the 4 GMTs and 4 SC NI statistical tests, based on a guidance of PPoS of less or equal _____, considering also the trend across the different PPoS calculated:
 - The individual PPoS to meet NI for each vaccine strain and each parameter (Geometric Mean Titre [GMT] and Seroconversion [SC] rate)
 - The overall PPoS of the 4 GMTs NI statistical tests
 - The overall PPoS of the 4 SC NI statistical tests
 - RIV4 immunogenicity results with regards to comparator in each age, priming status and baseline serological status subgroup will also be considered to inform the decision.
 - Safety results will also be reviewed.

A charter will be written to define the roles and responsibilities of every party in the conduct of the interim analysis, the FIC functioning, and the issuance of recommendation for stopping the study.

3.5.1 Safety

Considering the safety endpoints described in Section 2 and the corresponding calculation methods defined in Sections 4.2.1 and 4.2.2, safety summaries on data up to D29 after the last vaccination will be presented.

Solicited reactions (solicited injection site and systemic reactions), unsolicited AEs, SAEs, and AESIs will be summarized by age group and by vaccine group.

Furthermore, the following listings of safety collected during the 2022-2023 flu season will be generated and presented to FIC:

- All SAEs.
- All Grade 3 solicited ARs.
- All AEs leading to study discontinuation

3.5.2 Immunogenicity

Sanofi decided to assess the likelihood of success in this study at the end of study. Hence, it was decided to calculate the predictive power of each endpoint (GMT and SC) based on data collected at the end of the first season, which is the flu season 2022-2023.

The predictive power is defined as the probability that the final study result will be successful, given the data observed thus far – at the time of the interim analysis (4).

Confidential/Proprietary Information Page 24 of 40 In addition, the following summary statistics will be generated and presented:

- GMT for each strain at D01 and D29 or D57
- The geometric mean titer ratios (GMTR): geometric mean of the post-vaccination/pre-vaccination ratio for each strain
- Seroconversion rate at D29 or D57 based on the baseline titer at D01
- Proportion of participants with titers ≥ 1:40 (1/dilution [dil]) for each strain at D01 and D29 or D57.

The immunogenicity analysis will be conducted on the PPAS, and on FAS if the attrition rate from FAS to PPAS is greater than 10%.

3.5.2.1 Calculating the individual PPoS (GMTs and SC rates).

In-house, 2 SAS Macros are to be used in calculating PPoS based on simulations. The first SAS macro will calculate PPoS of GMT for each vaccine strain separately, and the second SAS macro will calculate PPoS of seroconversion rate for each vaccine strain separately.

All NI inferiority testing will be conducted as per Section 3.1.

The main steps to calculate the individual PPoS for GMT and SC rate are described in Table 3.3 and

Table 3.4 respectively.

Table 3.2 presents the current numbers of participants at main study timepoints considered in the analysis.

 Table 3.2: Study Design – Current Planned Number of Randomized Participants at Main

 Study Timepoints

		RIV4	IIV4
Study Planning	Number of participants to	$N_{\rm F} = 706$	$N_{\rm C} = 706$
(protocol & SAP)	be enrolled by the end of		
	the study		
Interim	Approximate number of	$N_{i1F} = 183$	$N_{i1C} = 183$
	participants enrolled up to		
	interim analysis		
Remainder of the	Approximate number of	$N_{rF} = N_F - N_{i1F}$	$N_{rC} = N_C - N_{i1C}$
Study	participants to be enrolled	(706-183=523)	(706-183=523)
	by the end of the study		

Main Steps	Steps' Definition of each of the 4 Antigens GMT separately
1	The total number of participants to be enrolled in the whole study is approximately 1412, randomized with a 1:1 ratio between RIV4 and IIV4 vaccine groups.
	The interim data includes 366 randomized participants, randomized with a 1:1 ratio between the vaccine groups. The PPAS will be used as the main analysis set for PPoS calculation.
	All the randomized participants in the remainder of the study are going to be generated with a 1:1 ratio between the vaccine groups.
2	 At the interim analysis: For each vaccine group and each strain calculate the mean and standard deviation of LOG10(titer) use the predictive distribution to derive B times datasets (e.g. 100.000) of the participants not yet enrolled in the study (to reach the approximately 1200 planned PPAS subjects overall in both vaccines) – with a seed value in SAS of 1545313 (for RIV4) and 4878646 (for IIV4)
3	Combine the interim dataset and the B datasets of the after interim to constitute the final and complete B datasets using the same sequence number. The final complete B datasets will be used to derive the 2-sided 95% CI of the difference (between RIV4 and IIV4) between the LOG10(mean) of each antigen for each one of the B complete datasets.
4	Use the 2-sided 95% CI of the difference (between the mean LOG10(titer) of RIV4 and the mean of LOG10(titer) of IIV4) for each B dataset to calculate the PPoS by deriving the proportion of datasets with the NI success.
	NI success in each complete dataset of each vaccine strain will be determined by comparing the lower bound of the 95% CI to the NI margin (-0.176)

Table 3.3: Description and Definition of the Main Steps in Calculating PPoS for NI Based onGMTs for each Vaccine Strain, Separately

Main Steps	Steps' Definition of each of the 4 vaccine Strains separately
1	The total number of participants to be enrolled in the whole study is approximately 1412, randomized with a 1:1 ratio between RIV4 and IIV4 vaccine groups.
	The interim data includes 366 randomized participants, randomized with a 1:1 ratio between the vaccine groups. The PPAS will be used as the main analysis set for PPoS calculation.
	All randomized participants in the remainder of the study are going to be generated with a 1:1 ratio between the vaccine groups.
2	At the interim analysis:
	 For each vaccine group and each strain, calculate the proportion P_{RIV4} and the proportion P_{IIV4} corresponding the SC rates use the predictive distribution of these parameters to derive B times datasets (e.g. 100.000) of the participants not yet enrolled in the study (to reach the approximately 1200 planned PPAS subjects overall in both vaccines) – with a seed value in SAS of 1545313 (for RIV4) and 4878646 (for IIV4)
3	Combine the interim datasets and the B datasets of the after interim to constitute the final and complete B datasets using the same sequence number. The final complete B datasets will be used to deriving the 2-sided 95% CI of the difference between SC of each antigen for each one of the B complete datasets.
4	Use the 2-sided 95% CI of the difference (between SC of RIV4 and SC of IIV4) for each B dataset to calculate the PPoS by deriving the proportion of datasets with the NI success.
	NI success in each complete dataset will be determined by comparing the lower bound of the 95% CI to the NI margin

Table 3.4: Description and Definition of the Main Steps in Calculating PPoS for NI Based on SC rates for each Vaccine Strain, Separately

The age of subjects was stratified into 2 strata, planning to reach approximately 50% of subjects of age 2 to 5 years, and approximately 50% of subjects of age 6 to 8 years.

Each age subgroup was stratified into 2 strata, planning to reach approximately 50% of subjects primed, and approximately 50% of subjects who are unprimed.

Confidential/Proprietary Information Page 28 of 40

VV-CLIN-0628295 5.0

Hence, 4 subsets (2 age subgroup times 2 vaccination status) of subjects were formed. Each subset should include approximately 25% of subjects to be vaccinated in this study.

If the distribution of the study subsets in the interim PPAS dataset is substantially different from what was planned in the protocol, which is approximately 25% of subjects in each subset, a complementary calculation of PPOS may be performed, thus running the above steps 1 and 2 in each of the 4 subsets to reach 300 PPAS subjects overall in each subset (age subgroup and vaccination status), and adding an extra step 2bis, concatenating the 4 strata within each of the B datasets, before performing step 3 and step 4.

3.5.2.2 Overall PPoS of the 4 GMTs, and overall PPoS of the 4 SCs, and Study overall PPoS (4 GMTs and 4 SC rates)

Correlations between vaccines' strain titers are generally low. Hence, the overall PPoS for NI of the 4 GMTs will be calculated by multiplying the 4 individual PPoS for NI calculated based on the GMTs. Likewise, the overall PPoS for NI of the 4 SCs will be calculated by multiplying the 4 individual PPoS for NI calculated based on SCs.

The study overall PPoS will be calculated by multiplying the 8 individual PPoS (GMTs and SC rate) calculated above.

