7.2 Participant Discontinuation/Withdrawal from the Study

- A participant may be withdrawn from the study at any time at his/her parent(s)/legally acceptable representative own request or may be withdrawn at any time at the discretion of the investigator for safety, behavioral, or compliance reasons. This is expected to be uncommon.
- The reason for withdrawal should be clearly documented in the source documents and in the CRF: Adverse Event, Lost to Follow-up, Protocol Deviation, or Withdrawal by Parent / Legally Acceptable Representative.

- The participant will be permanently discontinued both from the study intervention and from the study at that time.
- If the participant's parent(s)/legally acceptable representative withdraw(s) consent for disclosure of future information, the Sponsor may retain and continue to use any data collected before such a withdrawal of consent.
- If a participant's parent(s)/legally acceptable representative withdraw(s) consent, they may request destruction of any biological samples taken (unless local law requires not to destroy them), and the investigator must document this in the site study records.
- Withdrawn participants will not be replaced.

Follow-up of Discontinuations

For participants who have prematurely terminated the study, the site should attempt to contact them and complete all scheduled safety follow-ups, except if they specified that they do not want to be contacted again and it is documented in the source document.

For participants where the reason for early termination is lost to follow-up, the site will not attempt to obtain further safety information. See Section 7.3 for definition of "lost to follow-up".

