3.1 Statistical Hypotheses

Primary Objective:

Statistical Methodology for analyzing the primary 8 endpoints of geometric mean titers (GMTs) and SC rates.

NI of RIV4 as compared to IIV4 in participants 3 to 8 years of age will be conducted for GMTs and SC rates.

For each strain, the NI methodology will be applied to compare the post-vaccination GMTs and the SC rates between the groups using a 1-sided Type I error rate of 0.025 with the given individual hypothesis.

The primary analysis will be conducted into 2 steps starting with testing for NI of GMTs between RIV4 and IIV4. If NI of GMTs based on the 4 strains is demonstrated, then NI for SC will be also tested.

Step1: Geometric Mean Titers

For each of the 4 strains, the hypotheses are as follows. Each of the 4 individual H0 need to be rejected to demonstrate NI in GMTs.

 $H_0: GMT_{RIV4} / GMT_{IIV4} \leq 0.667$ $H_A: GMT_{RIV4} / GMT_{IIV4} > 0.667$

or equivalently,

H₀: $\log_{10} (GMT_{RIV4}) - \log_{10} (GMT_{IIV4}) \le \log_{10} (0.667)$ H_A: $\log_{10} (GMT_{RIV4}) - \log_{10} (GMT_{IIV4}) \ge \log_{10} (0.667)$

Step 2: Seroconversion

Confidential/Proprietary Information Page 15 of 40 For each of the 4 strains, the hypotheses are as follows. Each of the 4 individual H0 need to be rejected to demonstrate NI in SCs.

H₀: P _{RIV4} - P _{IIV4} \leq -10% H_A: P _{RIV4} - P _{IIV4} \geq -10%

Secondary Objectives:

There are no statistical hypotheses to be tested in the secondary objectives.

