3.2 Sample Size Determination

A total of approximately 1200 evaluable participants 3 to 8 years of age will be assessed (approximately 50% participants enrolled in the age group 3-5 years and 50% participants enrolled in the age group 6-8 years) in this study. Approximately 50% of participants enrolled within age group will be primed, and the other 50% will be unprimed.

Assuming similar GMTs in both groups and a standard deviation of log titers of 0.6 with a NI margin of 1.5 (or 1/1.5 = 0.667); NI for GMTs would be demonstrated with a power of approximately 99.6%.

Assuming in each vaccine group the same expected SC rates (0.5, 0.5, 0.7, 0.7) for each of the 4 strains (A/H1N1, A/H3N2, B/Yamagata and B/Victoria), based on conservative estimates from historical data, and a NI margin of 10%, the NI for SC can be demonstrated with a statistical power of approximately 82.0% (93.7%, 93.7%, 96.7% and 96.7% for each strain, respectively).

Hence, the overall study power is estimated to be approximately 82.0% (82.0% = 99.6%[GMTs] x 82.0%[SC]).

As shown above, to keep the study power above 80%, the sample size was increased accordingly, to have an overall Type II error <20% for the 8 NI tests.

Assuming 15% attrition rate in this age group; a total of approximately 1412 participants 3 to 8 years of age will be enrolled in this study.

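### The PPoS simulation fixes the final PPAS at about 1200 whatever the interim retention, so the later retention it implies moves opposite to the retention observed

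*SAP*

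**What the plan says.** SAP 3.2 sets the design size: "A total of approximately 1200 evaluable participants 3 to 8 years of age will be assessed", and "Assuming 15% attrition rate in this age group; a total of approximately 1412 participants 3 to 8 years of age will be enrolled". SAP Table 3.2 splits the enrolment into 183 per arm at the interim and 523 per arm still to come, 1046 in all.

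In step 1 of SAP Tables 3.3 and 3.4 the PPAS is the main set for the PPoS. Step 1 of Table 3.3 adds: "All the randomized participants in the remainder of the study are going to be generated with a 1:1 ratio between the vaccine groups"; Table 3.4 has nearly the same sentence. Step 2 of both tables simulates the children not yet enrolled "to reach the approximately 1200 planned PPAS subjects overall in both vaccines". If the interim mix of age and vaccination strata departs from plan, SAP 3.5.2.1 allows a complementary calculation that fills each of the four subsets to 300 PPAS children, again 1200 in total.

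SAP 3.5.2 defines predictive power as "the probability that the final study result will be successful, given the data observed thus far". Protocol 7.2 states: "Withdrawn participants will not be replaced". Neither table lets the projected final PPAS size depend on how many season-1 children qualified.

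**The concern.** A predictive power figure should describe the trial likely to be completed, given what has been seen. By the interim, the share of randomized children who qualify for the PPAS is known for season 1. Step 2 uses that share only to set how many children must be added. With the total held at 1200, each child missing from the interim PPAS is made good by one more simulated child from the same 1046 still to be randomized. A season with poor retention is thus followed, in the simulation, by one with better retention, and the reverse.

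The overall PPoS is the first criterion listed for the FIC in SAP 3.5 and 3.5.2.3. It is compared with a guidance threshold, so a shift of a few points could matter if the result lies close to it.

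**Working it through.** **Inputs.** From SAP 3.1 and 3.2: each test is run "using a 1-sided Type I error rate of 0.025 with the given individual hypothesis"; "a standard deviation of log titers of 0.6 with a NI margin of 1.5" (log10 scale, per Protocol 9.2); seroconversion (SC) rates 0.5, 0.5, 0.7 and 0.7 in both arms with a 10-point margin; 1200 evaluable and 1412 enrolled. From SAP Tables 3.2 to 3.4: 366 randomized at the interim and 1046 to come. From SAP 3.5.2.2: overall PPoS is the product of the eight individual values. Assumptions: interim PPAS retention r, which the documents do not give, over 60% to 95%; zero observed difference on every strain; flat prior.

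**Design figures.** 1200/0.85 = 1412. At 600 per arm, GMT power is 99.91% per strain and 99.6% for four, as stated. By a normal approximation SC power is 93.4% and 96.6% per strain and 81.3% jointly (stated: 93.7%, 96.7% and 82.0%). Overall it is 81.0% (stated: 82.0%). The method agrees with the plan to within about one point.

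**Implied later retention.** Step 2 needs 1200 - 366r children from 1046, so the implied retention is (1200 - 366r)/1046. Carrying r forward gives 1046r later PPAS children and 1412r in the final PPAS. The two rules coincide at r = 1200/1412 = 85%.

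| r | Interim PPAS | Added by step 2 | Implied later retention | Added at r | Final PPAS at r |
|---|---|---|---|---|---|
| 90% | 329 | 871 | 83.2% | 941 | 1271 |
| 85% | 311 | 889 | 85.0% | 889 | 1200 |
| 80% | 293 | 907 | 86.7% | 837 | 1130 |
| 75% | 274 | 926 | 88.5% | 784 | 1059 |
| 70% | 256 | 944 | 90.2% | 732 | 988 |
| 60% | 220 | 980 | 93.7% | 628 | 847 |

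**PPoS.** Let n1 = 183r be the interim PPAS per arm, N the final PPAS per arm, n2 = N - n1, and v the variance (0.36 for log10 titer; 0.25 or 0.21 for SC). The final difference has predictive SD sqrt(2·v·n2/(N·n1)). Success requires it to exceed -margin + 1.96·sqrt(2v/N), with margin 0.176 (log10) or 0.10.

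Example at r = 75%, strain with SC rate 0.5, n1 = 137.25:
- 1200 rule, N = 600: SD 0.0530, threshold -0.0434, PPoS Φ(0.0434/0.0530) = 0.794.
- Retention carried forward, N = 529.5: SD 0.0519, threshold -0.0398, PPoS 0.778.

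The other components at r = 75% are 0.955 and 0.952 for each GMT, and 0.839 and 0.827 for SC rate 0.7. The product, GMT⁴ × SC(0.5)² × SC(0.7)², is 0.369 under the 1200 rule and 0.339 with carry-forward.

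| r | Overall PPoS, 1200 rule | Overall PPoS, retention carried forward |
|---|---|---|
| 95% | 0.48 | 0.51 |
| 90% | 0.46 | 0.47 |
| 85% | 0.43 | 0.43 |
| 80% | 0.40 | 0.38 |
| 75% | 0.37 | 0.34 |
| 70% | 0.34 | 0.29 |
| 60% | 0.28 | 0.21 |

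**Checks.** A beta-binomial simulation with the Wilson score interval, SC rate 0.5 and r = 70%, gives 0.788 against 0.758; the formula gives 0.783 against 0.758. With an observed GMT ratio of 0.9 and SC 3 points lower on every strain, overall PPoS is 0.078 against 0.070 at r = 80% and 0.066 against 0.046 at 70%: same direction, smaller absolute gap.

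**The case against.** **Conditioning on the planned size is a legitimate choice.** The SAP states it openly, and its definition of predictive power does not say that the final sample must be re-forecast. Projecting season-1 retention onto a later season is itself an assumption. This stands, and it is why the planned-1200 figure should be kept beside the other.

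**The tables might be thought to give two conflicting simulation counts.** A reader could add the 1046 of step 1 to 311 interim PPAS children, get 1357, and set that against the 1200 of step 2. The documents do not support this. Table 3.2 and step 1 count randomized children, and step 2 gives the operative PPAS size, which the 300-per-subset rule confirms. At the planned 15% attrition the counts agree: 1046 × 0.85 = 889 = 1200 - 311. Only a clarifying sentence is needed.

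**It might be inferred that observed retention is ignored altogether.** It is not. Fewer interim PPAS children widen the predictive distribution. At r = 75% the SAP's own rule already lowers the PPoS from 0.428 to 0.369, and carrying retention forward takes it to 0.339. That is 0.059 of a total drop of 0.089, about two-thirds. Only the projection to the final size is missing.

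**Enrolment might be read as capped at 1412.** Both documents say approximately 1412, and the rule in Protocol 7.2 bars replacing individuals without setting a ceiling. The implied retention figures hold for the planned enrolment, not for a fixed maximum.

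**Some mitigation exists.** SAP 3.5.2 adds an immunogenicity analysis on the FAS if attrition from FAS to PPAS exceeds 10%. That can show the FIC that per-protocol retention is poor, but it does not alter the projected sample size in the PPoS.

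**Conclusion.** The point holds as a minor one. With about 1412 enrolled, no replacement and a fill-up to about 1200, the implied later retention falls as observed retention rises. The PPoS is mildly optimistic when interim retention is below 85% and mildly pessimistic above it. Under zero observed difference and the design SD and SC rates, the gap is about 1.5 points at 80%, 3 at 75%, 4.5 at 70% and 7 at 60%. It is zero at 85% and reverses to about 1.4 points at 90%.

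A reader might infer that the futility recommendation would have been different. The documents cannot support that: the interim PPAS count is not given, the threshold is redacted, and SAP 3.5.2.3 treats it as guidance weighed with trends, subgroup results and safety. The interim analysis allows stopping for futility or safety only, so the type I error of the final tests is not inflated.

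**What to change.** In step 2 of Tables 3.3 and 3.4, set the number of simulated PPAS children per arm to 523 times the PPAS retention observed at the interim, pooled over arms. Report the planned-1200 version beside it under its own label. Treat the complementary calculation the same way: in each subset, apply the observed retention to the children still to be randomized (planned 1412/4 = 353, less those already randomized), and show the 300-per-subset version alongside. Add one sentence saying that the counts in Table 3.2 and step 1 are randomized children, not the number of PPAS records simulated.

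The cost is a short SAP edit and about one line in each macro. The PPoS will be slightly less favourable if retention is below 85%. Trial conduct, margins and the final analysis are unchanged.
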